4.1.3 Selection of doses in the trial

The exposure response relationship between empagliflozin and UGE was evaluated for patients with T1DM (for further details please refer to Section 1.2.2). Results indicate that near maximal effects are achieved with empagliflozin 10 mg and 25 mg once daily; these findings are comparable to those observed in patients with T2DM. It is concluded that there are no clinically relevant differences in PK/PD between the T1DM and T2DM populations and that the approved doses for T2DM patients are appropriate for use in studies assessing

Page 37 of 122

Proprietary confidential information © 2016 Boehringer Ingelheim International GmbH or one or more of its affiliated companies

the safety and efficacy of empagliflozin in adult patients with T1DM. A detailed comparison of empagliflozin PK/PD in patients with T1DM versus T2DM is provided in Section 1.2.2.3.

In addition, an empagliflozin 2.5 mg dose group is included into this trial to establish a minimal safe and effective dose for the treatment of patients with T1DM.

For further details with respect to T2DM PK/PD, please refer to Section 1.2.2.1 and to the current version of the IB for empagliflozin [c01678844].

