7.3.4 Safety analyses

Safety will be assessed for the endpoints listed in Section 5.1.3.2. All treated patients will be included in the safety evaluation (i.e. in the TS). Safety analyses will assign patients to the treatment group as randomised. Safety analyses will be mostly descriptive in nature and will be based on BI standards. In addition, statistical analysis for selected endpoints (to be defined in the TSAP) may be performed, if appropriate. No hypothesis testing is planned.

The active empagliflozin treatment groups will be compared with the placebo group in a descriptive way. Tabulations of frequencies/proportions will be used for the evaluation of categorical (qualitative) data, and tabulations of descriptive statistics will be used to summarise continuous (quantitative) data.

Adverse events will be coded using the Medical Dictionary for Drug Regulatory Affairs (MedDRA). The analysis of AEs will be based on the concept of treatment emergent adverse events. That means that all AEs occurring from first study medication intake until 7 days after last study medication intake will be assigned to the randomised treatment. This includes AEs that start before first study medication intake and deteriorate under treatment. All AEs occurring before first study medication intake will be assigned to 'pre-treatment' and all AEs occurring after last study medication intake + 7 days will be assigned to 'post-treatment'. Additional listings based on actual treatment at onset of AE will be produced for patients who receive incorrect treatment at any point during the trial. Specific analyses of hypoglycaemia will assign events only up to the end of the last study medication intake + 1 day to the randomised treatment, later hypoglycaemia events will be assigned to 'post-treatment'.

Frequency, severity, and causal relationship of AEs will be tabulated by system organ class and preferred term after coding according to the current version of the MedDRA.

Independent of this rule, the relationship of an AE to the study medication will be assessed by the Investigator.

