Statistical parameters will be displayed to a defined number of decimal places as specified in the BI guideline "Reporting of Clinical Trials and Project Summaries" ([7](#)).

Tabulations of frequencies for categorical data will include all possible categories and will display the number of observations in a category as well as the percentage (%) relative to the respective treatment group (unless otherwise specified, all patients in the respective patient set whether they have non-missing values or not). Percentages will be rounded to one decimal place. The category missing will be displayed only if there are actually missing values.

Treatment comparison

In all specified statistical analyses, treatment comparisons will be made between each randomised Empagliflozin group (2.5, 10 and 25 mg) and placebo.

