A second frequency analysis will be created and will display the characteristics of ketoacidosis for patients with CEC certain ketoacidosis. These characteristics will include outcome, severity of the worst episode, time to onset of first episode, and lowest blood pH. This analysis will be successively repeated for ketoacidosis endpoints considered by the CEC as potential, as well as for ketoacidosis endpoints considered by the CEC as certain or potential.

Time to onset of the first CEC certain ketoacidosis event will be analysed by Kaplan-Meier estimates. The onset date determined by the adjudication committee will be used as date of event. The time to the occurrence of the event will be computed as date of the event minus date of first drug intake plus one day.

The Kaplan-Meier graph will present data up to the end of the treatment period.

Patient without an event will be considered censored at the date of the last trial drug intake plus seven day.

A log-rank test will be then computed to test the equality of the survival curves.

The Kaplan-Meier analysis and the log-rank test will then be performed for CEC certain or potential ketoacidosis event.

Frequency of patients with CEC certain ketoacidosis (and respectively CEC potential ketoacidosis) will be planned by preferred term from the specified trigger search terms for DKA.

- Analysis of frequency of ketoacidosis episodes

An overview table will first summarize the results of the CEC adjudication committee on ketoacidosis episodes by worst severity.

The CEC certain ketoacidosis episodes will be tabulated by treatment and characteristics of ketoacidosis (e.g. outcome, severity, pre-existing factors, blood pH).

When appropriate, the number of episodes per 100 patient-years will be calculated in addition to the number of episodes according to the following formula:

$100 * (\text{number of ketoacidosis events} / \text{time at risk [patient-years]})$ to report a diabetic ketoacidosis event)

Where time at risk [patient-years] is calculated as time from first administration of study drug until last administration of study drug + 7 days, summed up over all patients per treatment group, and divided by 365.25.

The same ketoacidosis episode analysis will be presented for CEC potential ketoacidosis, as well as for CEC certain or potential ketoacidosis.

- Other ketoacidosis endpoints

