The Kaplan-Meier graph will present data up to the end of the treatment period.

Patient without an event will be considered censored at the date of the last trial drug intake plus one day.

A log-rank test will be computed to test the equality of the survival curves.

Patients with CEC confirmed severe hypoglycaemia will be tabulated by treatment and characteristics of hypoglycaemia including minimum glucose level and time to onset of first episode. The frequency of severe nocturnal hypoglycaemia AE (i.e. any hypoglycaemia event with an onset from 0:00 midnight to 5:59 a.m.) will also be evaluated as part of these characteristics.

Finally, the severe hypoglycaemia considered serious or requiring third person assistance will be tabulated using the narrow SMQ Hypoglycaemia. This analysis will be restricted to patients with CEC confirmed severe hypoglycaemia.

- Analysis of frequency of hypoglycaemia adverse events

The number of CEC confirmed severe hypoglycaemic episodes will be first tabulated by treatment and characteristics of hypoglycaemia. When appropriate, the number of episodes per patient-year will be provided in this analysis. The time at risk for severe hypoglycaemia [patient-years] will be derived similarly as for ketoacidosis, but in using 1 day of washout instead of 7 days in the calculation.

A negative binomial model will be fitted to analyse the event rate of CEC confirmed severe hypoglycaemia per patient-years, with terms for treatment, continuous baseline rate, continuous baseline HbA1c, continuous baseline eGFR (CKD-EPI, creatinine) and pre-existing insulin therapy as fixed effects and log(time at risk) as an offset.

In addition, the severe hypoglycaemic episodes that have been confirmed by the adjudication committee will be represented on a graph by hour of the day (from midnight to 11:59 pm).

- Investigator defined AESI severe hypoglycaemia adverse event endpoint

Patients with investigator defined AESI severe hypoglycaemia will also be summarised by treatment and event characteristics, as well as the investigator defined AESI severe hypoglycaemic episodes.

Patients with investigator defined AESI severe hypoglycaemia will additionally be summarised by SOC, PT and treatment group.

Lower limb amputation

A frequency table summarising the investigator defined AESI lower limb amputation events will be created by SOC and PT. The table will be then repeated for serious events, and for events leading to treatment discontinuation.

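### For ketoacidosis the SAP plans a log-rank test but no dose-versus-placebo effect estimate or confidence interval, so the planned comparison cannot bound the excess risk at any dose

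*SAP*

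**What the plan says.** **Ketoacidosis (SAP 7.8.1.4).** The planned outputs are frequency tables of CEC results, Kaplan-Meier estimates of time to first CEC-certain event, and event characteristics by treatment. For rates: "When appropriate, the number of episodes per 100 patient-years will be calculated in addition to the number of episodes", with time at risk running from first dose to last dose plus 7 days and summed within each treatment group. On comparison between groups the text has one sentence: "A log-rank test will be then computed to test the equality of the survival curves". The Kaplan-Meier analysis and the test are then repeated for certain-or-potential events. Contrasts, alpha and sidedness are not given.

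**Severe hypoglycaemia (same section).** The wording is almost the same: "A log-rank test will be computed to test the equality of the survival curves". Here, however, the SAP adds: "A negative binomial model will be fitted to analyse the event rate of CEC confirmed severe hypoglycaemia per patient-years, with terms for treatment", together with baseline covariates and a time-at-risk offset.

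**General rule (SAP 7, Treatment comparison).** "In all specified statistical analyses, treatment comparisons will be made between each randomised Empagliflozin group (2.5, 10 and 25 mg) and placebo".

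**Protocol.** Section 7.3.4 calls safety analyses mostly descriptive, lets the SAP define statistical analyses for selected endpoints, and then says: "No hypothesis testing is planned". Section 4.1.3 says the 2.5 mg arm is included "to establish a minimal safe and effective dose for the treatment of patients with T1DM".

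**The concern.** The protocol (2.3 and 4.2.1) describes ketoacidosis as a risk that could be life-threatening and that empagliflozin may make harder to recognise. The useful safety statement is therefore dose-specific: how large an excess over placebo is compatible with the data at 2.5, 10 and 25 mg. The 2.5 mg arm in particular was added with safety in mind.

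The planned comparison does not deliver that statement on either reading.

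- **Four-arm reading.** The null is that all curves are equal. A small p-value does not say which dose differs from placebo, or even whether placebo is involved.
- **Pairwise reading.** Each dose gets a p-value against placebo, but no effect size and no upper limit.

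A p-value above 0.05 on a handful of events could then be taken as reassurance when the data are compatible with a large excess. The SAP does fit a treatment-effect model for severe hypoglycaemia and for lipids, so the omission for ketoacidosis stands out.

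**Working it through.** **1. What the plan is sized for.** Protocol 7.7 sizes the trial on HbA1c only: difference 0.3, SD 0.9, two-sided alpha 0.025. A noncentral t calculation gives 225 per arm with 90.0% power, as stated, and 225/0.94 = 239.4, i.e. 240 per arm. No event count, rate or power is given for ketoacidosis. All event figures below are therefore assumptions.

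**2. Time at risk.** A completer contributes about 182 + 7 = 189 days. At most, 240 × 189/365.25 = 124 patient-years accrue per arm. Equal time at risk in the two arms is assumed from here on.

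**3. Exact rate ratio.** With x1 events on a dose and x0 on placebo, and equal time at risk, x1 given the total is binomial with proportion p, and the rate ratio is p/(1 − p). Put the Clopper-Pearson 95% limits for p into that expression.

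- 2 v 2: limits for 2/4 are 0.0676 and 0.9324. The ratio is 1.0, from 0.0676/0.9324 = 0.07 to 0.9324/0.0676 = 13.8.
- 8 v 3: limits for 8/11 are 0.390 and 0.940. The ratio is 8/3 = 2.67, from 0.390/0.610 = 0.64 to 15.6 (using the unrounded upper limit 0.9398).

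**4. Risk difference.** Newcombe interval from Wilson limits, 240 per arm with complete follow-up.

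- 8/240 = 3.33% (1.70 to 6.44); 3/240 = 1.25% (0.43 to 3.61); difference 2.08 points.
- Lower limit: 2.08 − √[(3.33 − 1.70)² + (3.61 − 1.25)²] = −0.8.
- Upper limit: 2.08 + √[(6.44 − 3.33)² + (1.25 − 0.43)²] = +5.3.

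| Events, dose v placebo | Exact rate ratio (95%) | Risk difference, points (95%) |
|---|---|---|
| 2 v 2 | 1.0 (0.07 to 13.8) | 0.0 (−2.2 to 2.2) |
| 5 v 3 | 1.67 (0.32 to 10.7) | 0.8 (−1.8 to 3.7) |
| 8 v 3 | 2.67 (0.64 to 15.6) | 2.1 (−0.8 to 5.3) |
| 10 v 3 | 3.33 (0.86 to 18.8) | 2.9 (−0.1 to 6.3) |

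For 8 v 3, Fisher's exact p is 0.22. Under the current plan the reader would see a non-significant p-value beside two rates, and not that a rate ratio near 15 is still compatible with the data.

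**5. Events needed for a pairwise log-rank test.** Schoenfeld's formula at two-sided 5% and 80% power is 4(1.96 + 0.842)²/(ln HR)². It gives 66 events for HR 2, 27 for HR 3 and 17 for HR 4, across the two arms together.

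**6. What a four-arm p-value conveys.** Simulation: 4,000 trials, 240 per arm, exponential times, no dropout, two-sided 5%. Assumed risks are 1% on placebo and 2.5 mg, and 4% on 10 and 25 mg. The 3-df test rejects in 72% of trials. The pairwise tests reject in 57% for each higher dose and in about 5% for 2.5 mg. The 72% is power against a null that is false, so those rejections are correct. The point is only that the result does not identify the dose.

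**The case against.** Several arguments on the other side are sound.

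- **A reader might infer that one four-arm test is planned.** The documents do not establish this. The log-rank sentences leave the contrasts open, and the general rule in SAP 7 supports dose-versus-placebo comparisons. The defect is an unstated contrast, not a confirmed omnibus test. It follows that the 72% figure is not an error rate and does not apply at all under the pairwise reading.
- **A reader might infer that severe hypoglycaemia also lacks an effect measure.** It does not. The negative binomial model has a treatment term and yields a rate ratio for each dose versus placebo. Only an explicit commitment to report its interval is missing.
- **The p-value is not the only output.** By-group counts, Kaplan-Meier estimates and episode rates are planned, and a reader could build a crude interval from the counts.
- **Low power comes from the trial's size.** With assumed risks of 1% and 3%, a pairwise test has about 33% power. No choice of method changes that.
- **Protocol 7.3.4 is not a flat prohibition.** It lets the SAP add statistical analyses for selected endpoints, and SAP 7.8.1 keeps adverse event analyses descriptive unless otherwise specified.

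What remains is this: SAP 7.8.1.4, whose text shows no redaction, names no between-group estimate or interval for ketoacidosis. Low power strengthens the case for an interval, because the interval shows what the trial cannot exclude. A log-rank test is also still a hypothesis test, so the tension with the protocol sentence needs a label.

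**Conclusion.** The point holds for ketoacidosis, under both the certain and the certain-or-potential definitions. The only planned between-group statistic is a log-rank p-value, which cannot bound the excess risk at any dose whether it is read as four-arm or as pairwise. With event counts of the order assumed here, the omitted upper limits are large: rate ratios of about 11 to 19 and risk differences of about 2 to 6 points.

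These sizes rest on assumed counts, 240 patients per arm and equal time at risk; the documents supply no event rates. The stronger conclusions, that the trial would wrongly condemn 2.5 mg or that severe hypoglycaemia is equally uncovered, are not supported. The tests lie outside the confirmatory hierarchy, so type I error control for HbA1c and the key secondary endpoints is unaffected. This is an inexpensive improvement to the safety analysis, not a flaw in the trial's main inference.

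**What to change.** In SAP 7.8.1.4:

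1. For each dose versus placebo, and for both ketoacidosis definitions, report a rate ratio with an exact 95% interval using the time at risk the SAP already defines, or a Firth-penalised hazard ratio with its 95% interval. For the exact ratio, count one first event per patient, because repeat episodes in one patient would make the interval too narrow.
2. Report the Week 26 risk difference from the Kaplan-Meier estimates with a 95% interval, so that patients who stop early are not counted as event-free. Say in advance how an arm with no events is handled, since the usual Kaplan-Meier standard error is then zero.
3. State that the 95% interval for the severe-hypoglycaemia rate ratio from the negative binomial model will be reported.
4. If the log-rank tests are kept, define them as pairwise against placebo, in line with SAP 7, and label the p-values nominal. Add a sentence reconciling them with Protocol 7.3.4.

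The cost is a few sentences and one added table per endpoint, with no new data. The intervals will be wide when events are few, and will show how little the trial can exclude.

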7.8.1.5 Other specific adverse events

Hypoglycaemia

- Hypoglycaemia adverse events

In this sub-section, only hypoglycaemia reported by the investigator as adverse events will be discussed. For specifications on analyses on severe hypoglycaemia adverse event, refer to [Section 7.8.1.4](#).

Refer to [Section 9.3](#) for details on the derivation of the hypoglycaemia adverse event endpoints listed below.

Every episode of $PG \leq 70$ mg/dL should be documented with the respective time and date of occurrence. This includes hypoglycaemia with glucose values < 54 mg/dL and all symptomatic and all severe hypoglycaemic events. On the basis of this information the hypoglycaemic adverse event will be classified according to the following protocol defined categories:

- Asymptomatic hypoglycaemia with $PG \leq 70$ mg/dL
 - Documented symptomatic hypoglycaemia with $54 \text{ mg/dL} \leq PG \leq 70 \text{ mg/dL}$ and typical symptoms
 - Documented symptomatic hypoglycaemia with $PG < 54 \text{ mg/dL}$ and typical symptoms and no need for external assistance
 - Severe hypoglycaemia, events requiring assistance
- Analysis of number of patients with hypoglycaemia adverse events

The frequency of patients with protocol defined hypoglycaemia adverse event will be presented by treatment.

The frequency of patients with hypoglycaemia adverse event according to investigator's judgment will be tabulated by treatment, SOC and preferred term.

- Analysis of frequency of hypoglycaemic adverse events

Similarly as for the analysis on patient level, a summary on the number of protocol defined hypoglycaemia adverse event episodes will be produced per patient-years.

Then, descriptive statistics will be produced for the predefined protocol further safety endpoint “rate of symptomatic hypoglycemic AE with confirmed $PG < 54$ mg/dL and/or severe hypoglycaemic AE confirmed by the adjudication, per 30 days, from Week 1 to Week 4”. A negative binomial model with terms for treatment, baseline rate, continuous baseline HbA1c, continuous baseline eGFR (CKD-EPI, creatinine) and pre-existing insulin therapy as fixed effects and log (time at risk [30 days]) as an offset will also be prepared. These two analyses will furthermore be replicated on the FAS.

Step 1 and Step 2 of the TSAP [Section 5.4.7](#) collapsing rules will apply, in order to avoid the double-counting of episodes between adjudicated severe hypoglycaemia data and hypoglycaemia AE data.

- Patient-reported hypoglycaemia events

The endpoints describe in this sub-section will be exclusively based on patient-reported hypoglycaemia data.

A summary presenting the number of patients with the following endpoints will be tabulated:

- Asymptomatic hypoglycaemia with $PG \leq 70$ mg/dL
- Symptomatic hypoglycaemia with $PG \leq 70$ mg/dL
- Asymptomatic hypoglycaemia with $PG < 54$ mg/dL
- Symptomatic hypoglycaemia with $PG < 54$ mg/dL
- Nocturnal symptomatic hypoglycaemia with $PG \leq 70$ mg/dL
- Nocturnal symptomatic hypoglycaemia with $PG \leq 70$ mg/dL
- Nocturnal asymptomatic hypoglycaemia with $PG < 54$ mg/dL
- Nocturnal asymptomatic hypoglycaemia with $PG < 54$ mg/dL

The number of episodes per patient-year will be analysed for these endpoints as well, for which the TSAP [Section 5.4.6.3](#) collapsing rules will apply.

A negative binomial model will be fitted to analyse the symptomatic hypoglycaemia with $PG < 54$ mg/dL, with terms for treatment, continuous baseline HbA1c, continuous baseline eGFR (CKD-EPI, creatinine) and pre-existing insulin therapy as fixed effects and log(time at risk) as an offset.

Urinary and genital infections

The following additional specific adverse events will also be assessed and be tabulated by treatment group:

- Genital tract infections (narrow BICMQ, investigator assessment)
- Urinary tract infections (UTI) (narrow BICMQ, investigator assessment)

The serious genital infection events as well as the genital infection events leading to treatment discontinuation will additionally be summarised using the narrow project defined PT list.

Similarly, the serious UTI events as well as the UTIs leading to treatment discontinuation will be summarised using the BICMQ.

A frequency table for complicated urinary tract infections/pyelonephritis/urosepsis where 'complicated urinary tract infections' are defined as serious AEs from the narrow BICMQ UTI, all events included in the sub-BICMQ pyelonephritis and all events of preferred term urosepsis will in addition be provided .

Genital infections based on investigator assessment will additionally be summarised by type (fungal balanitis or fungal vulvovaginitis, genital infection other than fungal balanitis or fungal vulvovaginitis), intensity (mild, moderate or severe), time to onset of first episode (within the first 3 months of treatment or after), duration (<7 days, 7-14 days and >14 days), how the event was treated (no treatment, therapy assigned, hospitalisation), treatment (0, 1, 2, >2 antimicrobials needed to treat), duration of treatment (≤ 7 days, >7 days), whether leading to discontinuation of treatment, and the number of episodes per patient.

Furthermore, the above mentioned displays on genital infections based on investigator assessment will be repeated by the type of infection (fungal balanitis or fungal vulvovaginitis, or genital infection other than fungal balanitis or fungal vulvovaginitis).

UTIs based on investigator assessment will additionally be summarised by intensity (mild, moderate or severe), time to onset of first episode (within the first 3 months of treatment or after), duration (<7 days, 7-14 days and >14 days), anatomical location (upper UTI, lower UTI), how the event was treated (no treatment, therapy assigned, hospitalisation), treatment (0, 1, 2, >2 antimicrobials needed to treat), duration of treatment (≤7 days, >7 days), whether leading to discontinuation of treatment, and the number of episodes per patient.

Kaplan-Meier graphs will also be created for time to onset of the first investigator defined UTI and for time to onset of the first investigator defined genital infections. For both endpoints, the time to the occurrence of the event will be computed as date of the event minus date of first drug intake plus one day. The same censoring date rules as the ones defined in [Section 7.8.1.4](#) for time to onset to ketoacidosis endpoint will be used for patient without an event. The onset date of the first UTI episode will be used in case of multiple episodes.

The Kaplan-Meier graph will present data up to the end of the treatment period.

In the number of episodes analysis of UTI and genital infection AEs will be collapsed within each SSC regardless of preferred term with the collapsing following the description at the start of [Section 7.8.1](#) but the condensing will not be conducted in order to maintain multiple episodes per patient.

Acute pyelonephritis, sepsis, and asymptomatic bacteriuria

The following specific adverse event based on investigator assessment will be tabulated by treatment group:

- Acute Pyelonephritis: patient incidence overall and by intensity, and treatment required (0, 1, 2, >2 antimicrobials needed to treat)
- Sepsis: patient incidence overall and by source of infection
- Asymptomatic Bacteriuria: patient incidence overall

Bone fractures

Frequency of patients with bone fracture will be provided by event characteristics (e.g.type of fracture, intensity, and time to onset of first fracture). Bone fracture will also be displayed by SOC and PT using the BICMQ. The BICMQ analysis will be repeated for serious bone fracture events and for bone fractures leading to treatment discontinuation. Finally, the bone fracture events that occurred between first study drug intake and up to study end will be pooled together and analysed based on the BICMQ in a separate analysis.

Volume depletion

Frequency table of patients with volume depletion will be constructed based on preferred terms:

- Volume depletion: (BicMQ)

Malignancy

AE frequency table will be created for malignancies based on the following narrow SMQs:

- Malignancies: The following Sub-SMQs of SMQ Malignancies (20000090) will be used: Sub-SMQ Malignant or unspecified tumors (20000091) and Sub-SMQ Malignancy related conditions (20000092).

This analysis will be then replicated for serious malignancy, and for malignancy leading to treatment discontinuation.

Finally, all malignancy adverse events that occurred between first study drug intake up to study end will be pooled together and analysed based on the narrow SMQ search in a separate analysis.

